
8 SAFETY ANALYSES

All safety analyses will be carried out using the Safety Sample Set.

Descriptive statistics will be used to summarize all AEs and SAEs. Frequency and relative frequency will be used to present the number of subjects with AEs, SAEs, and with each specific event. We will explore the expected and unexpected adverse events.

8.1.1 Safety monitoring

Adverse events will be tracked for the WU site from the time of dose administration through two weeks post dose for drug related adverse events Laboratory testing (electrolyte panel, BUN, Cr, ALT, and AST) done as part of the study conducted at WU site, will be collected post dose within 12 hours. In the event the lab values are not within normal limits post dose, the PI will be notified and recommend that the subjects be evaluated by his/her treating physician. Study subjects will remain in the study and lab tests repeated until within normal limits. All adverse events will be documented and assessed for relatedness to the study medication.

The study team will monitor for adverse events on an ongoing basis. Once the team becomes aware of an adverse event, the AE will be reported according to institutional guidelines. Reporting requirements for Washington University study team may be found in Section 1.1 of protocol. Reporting requirements for secondary site study teams participating in Washington University-coordinated research may be found in Section 1.2 of protocol.

Early stopping rule related to serious adverse events: In the event of a serious adverse event, DSMB will evaluate the association of the serious adverse events with the study arm, break the blind if needed, and if found to be associated with treatment, DSMB will consider the study for revision or stopping.

8.2 Clinical Laboratory Tests

Biochemistry blood tests will be performed at screening for all subjects.

The following biochemistry laboratory parameters will be measured: Chloride, sodium, potassium, Carbon dioxide, Blood urea Nitrogen (BUN), creatinine, Alanine aminotransferase (ALT), Aspartate aminotransferase (AST).

Laboratory test results will be summarized descriptively by treatment group using Safety Analysis Sample.

All clinical laboratory results will be listed. Laboratory values that are outside the normal range will be flagged.

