## 5.5 Follow-Up Assessments

The follow-up assessments will occur after surgery and include the following tests or procedures:

- 1. DPOAE testing in recovery, within 8 hours after surgery.
- 2. Blood samples taken within 12 hours following the first pill for PGx surveys.
- 3. Collection of laboratory test results for research purposes that include an electrolyte panel, BUN, Cr, ALT, and AST. If these tests are not performed as part of clinical care post-operatively, we will obtain them for research purposes at the time of the PGx blood draw.
- 4. DPOAE, Audiogram, ECochG, and WIN testing 30 days (+/-3 days) after surgery.
- 5. Completion of the Hearing History and Occupation Exposure questionnaire 30 days (+/- 3 days) after surgery.
- 6. Documentation of adverse events.

Follow-up assessments will be planned at the stated time points; actual follow up times may vary due to patient logistics and compliance.

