## 8.0 REGULATORY AND REPORTING REQUIREMENTS

The entities providing oversight of safety and compliance with the protocol require reporting as outline below. Please refer to Appendix A for definitions and Appendix B for a grid of reporting timelines.

Adverse events will be tracked for the WU site from the time of dose administration through two weeks post dose and at the follow up 30 day visit for drug-related adverse events. All adverse events will be documented and assessed for relatedness to the study medication.

The study team will monitor for adverse events on an ongoing basis. Once the team becomes aware of an adverse event, the AE will be reported according to institutional guidelines. Reporting requirements for Washington University study team may be found in Section 8.1. Reporting requirements for secondary site study teams participating in Washington University-coordinated research may be found in Section 8.2.

In the event of a Serious Adverse Event determined by the PI to necessitate the breaking of the blind, the intervention assignment will be revealed by the independent programmer to the medical staff doctor caring for the patient. In the event the statistician is unable to be reached in a time needed, to assure the safety of the subject, the blind can be broken by [name] and information will be shared with the medical staff assuming care for the research subject.

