2.7 Sample Size Determination for The Primary Efficacy Outcome Measure

The primary efficacy outcome will be the proportion of PTS positive subjects defined as the ratio of PTS-positive subjects to total number of subjects in each study arm/group. Using pilot data from a retrospective chart review of 75 similar patients undergoing \geq 1-hour drill noise exposure, we estimate the proportion of PTS positive subjects in the placebo group will be 50%. We hypothesize that the expected effect of ZNS either pre-op or post-op will be a 50% reduction of the proportion of subjects with PTS positive as compared to placebo group. This is the desired clinically significant effect for treating hearing loss for single dose of 100 mg ZNS.

The sample size for this study was calculated for the planned comparisons of each of the ZNS groups with the placebo group using a balanced design and a one-sided alpha level of 0.0125 Based on the data from our retrospective study, using Fisher's exact test we estimated that 78 subjects in the ZNS group and 78 subjects in the placebo group will be needed to provide us with 80.4 % power to detect a 50% reduction in the proportion of PTS positive subjects *(from 50% to*

^{**}Dispensed on the day of surgery with instruction to take first dose prior to surgery and second dose after surgery.

^{***} Plasma sample for PGx will be collected at baseline visit. Plasma sample for ZNS level and PGx, electrolyte panel, BUN, Cr, ALT, and AST will be collected 12 hours after first dose.

25% corresponding to an absolute proportion difference of 25%) at the 1-sided alpha level of 0.0125 for each ZNS-Placebo group comparison. A total of 234 subjects will be enrolled to be randomized in this study. All efforts will be made minimize and eliminate drop outs. Given the short term-follow-up of study subjects in a period where they are under medical care, few, if any, drop-outs or lost to follow-up are expected.

Sample size calculations were carried out using PROC POWER procedure in SAS 9.4.

3 Study Outcomes

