4.3 The safety sample

The safety sample will include subjects from the full analysis population who will be enrolled and will receive active or placebo ZNS. Adherence to protocol does not affect inclusion in safety population. subjects are evaluated from the time of dose administration through two weeks post dose for drug related adverse events.

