Table 14.3.1.4	grades) by Maximum-reported Severity	Safety Sample Set
	Summary of Related Treatment Emergent Adverse	
Table 14.3.1.5	Events	Safety Sample Set
	Summary of TEAEs Leading to Study Drug	
Table 14.3.1.6	Interruption	Safety Sample Set
	Summary of TEAEs Leading to Study Drug	
Table 14.3.1.7	Withdrawn	Safety Sample Set
Table 14.3.2	Summary of Biochemistry Lab Results at Screening	Safety Sample Set
	Overall Summary of Physical Examination of Ears	
Table 14.3.3.1	Results at Screening	Safety Sample Set

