12.2 Index of Proposed Listings

Listing Number	Listing Title	Sample Set
Listing 16.1.1	Subject Enrollment and Disposition All Subjects	All Subjects
Listing 16.1.2.1	Subject Inclusion and Exclusion Criteria	All Subjects
Listing 16.1.2.2	Protocol Deviations	All Subjects
Listing 16.1.3	Demographic Characteristics	All Subjects
Listing 16.1.4	Medical and Surgical History	Safety Sample Set
Listing 16.1.5	Hearing History and Occupation Exposure	Safety Sample Set
Listing 16.1.6	Concomitant Medications	Safety Sample Set
Listing 16.1.7	Study Drug Administration	Safety Sample Set
Listing 16.2.1	Audiogram Results on Hearing Thresholds	ITT Sample Set
Listing 16.2.2	Distortion Product Otoacoustic Emissions (DPOAE) Results	ITT Sample Set
Listing 16.2.3	Electrocochleography (ECochG) Results ITT Analysis Set	ITT Sample Set
Listing 16.2.4	Word in Noise (WIN) Test Results ITT Analysis Set	ITT Sample Set
Listing 16.2.5	LENS-Q Adapted for Surgical Noise Study Results at Screening ITT Analysis Set	ITT Sample Set
Listing 16.3.1.1	Serious Adverse Events	Safety Sample Set
Listing 16.3.1.2	Adverse Events Resulting in Death	Safety Sample Set
Listing 16.3.1.3	Treatment-emergent Adverse Events	Safety Sample Set
Listing 16.3.1.4	Treatment-emergent Adverse Events leading to Study Drug Interruption	Safety Sample Set
Listing 16.3.1.5	Treatment-emergent Adverse Events leading to Study Drug Withdrawn	Safety Sample Set

Listing Number	Listing Title	Sample Set
Listing 16.3.2.1	Clinical Laboratory Results at Screening: Biochemistry	Safety Sample Set
Listing 16.3.2.2	Pregnancy Test at Screening	Safety Sample Set
Listing 16.3.3	Physical Examination of Ears at Screening	Safety Sample Set

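### A post-dose safety panel is drawn, but the SAP's named lab table and listing cover screening only, and both documents state the adverse event window inconsistently

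*SAP*

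**What the plan says.** **Laboratory data.** Protocol 5.5 lists among the follow-up assessments "Collection of laboratory test results for research purposes that include an electrolyte panel, BUN, Cr, ALT, and AST". The footnote to the Protocol 9.0 calendar places this draw within 12 hours of the first dose. SAP 8.1.1 agrees that the results "will be collected post dose within 12 hours" and acts on them: the PI is told of out-of-range values and the tests are repeated. The footnote to the SAP 2.6 calendar (printed in the text of 2.7) reads "Plasma sample for ZNS level and PGx, electrolyte panel, BUN, Cr, ALT, and AST will be collected 12 hours after first dose".

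The analysis section, SAP 8.2, opens with "Biochemistry blood tests will be performed at screening for all subjects" and names no other time point. It then says that results will be summarized by treatment group, that all results will be listed, and that out-of-range values will be flagged. The only lab table in SAP 12.1 is 14.3.2, "Summary of Biochemistry Lab Results at Screening". The only biochemistry listing in SAP 12.2 is 16.3.2.1, "Clinical Laboratory Results at Screening: Biochemistry".

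**Adverse events.** SAP 4.3 says that "subjects are evaluated from the time of dose administration through two weeks post dose for drug related adverse events"; SAP 8.1.1 and Protocol 6.0 give the same two weeks. Protocol 8.0 tracks events "from the time of dose administration through two weeks post dose and at the follow up 30 day visit for drug-related adverse events". Both calendars mark adverse event assessment at the 30-day visit. Protocol 11.1 and the opening of SAP 8 set no end date.

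**The concern.** Screening values precede treatment and cannot show an effect of it. A programmer who builds the outputs from the SAP index would produce a screening table and a screening listing, and the final report would hold no comparison by arm of any post-dose laboratory value. Protocol 7.1.7 and SAP 3.4 list metabolic acidosis among the serious side effects of ZNS, and the panel in SAP 8.2 includes carbon dioxide and chloride, so the data bear on a named risk.

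For adverse events, the main tables report treatment-emergent events, but the SAP never defines that term. Someone looking for a window in SAP 4.3 or 8.1.1 finds two weeks. Someone looking at the calendar finds the 30-day visit. The same event at day 25 could be counted or not, depending on which passage is followed.

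**Working it through.** No sample size, power or alpha figure is involved, so there is no stated figure to reproduce. The check sets the passages side by side, with two small pieces of arithmetic.

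**1. Lab outputs named in SAP 12.1 to 12.3**

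| Output | Visit named | Post-dose values by arm? |
|---|---|---|
| Table 14.3.2 | Screening | No |
| Listing 16.3.2.1 | Screening | No |
| Figure 14.1.2 (QQ plot) | None | No; a normality check |

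Named tables and listings for biochemistry: 1 + 1 = 2. Those that cover the post-dose draw: 0.

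**2. Is the titling just loose?** Two features of the SAP suggest not. The same index announces actual values and change from baseline for the audiogram, DPOAE, ECochG and WIN tables, so change outputs are named where they are intended. The ear examination table is also titled for screening, and SAP 8.3 confirms that this examination is done only then. The ordinary reading of the lab titles is therefore screening only. That conflicts with the rule in SAP 8.2 that all laboratory results be listed, and with SAP 5.1, which puts all assessments in the listings.

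**3. What a post-dose table could show in each arm.** Put the first capsule at hour 0 and the end of surgery at hour S.
- Draw: after surgery and within 12 hours of the first capsule (Protocol 5.6 and 9.0), so between S and 12.
- Second capsule: within 12 hours after surgery, or on release to oral medication (Protocol 5.2), so between S and S + 12, or on release.
- Pre-op arm: ZNS is the first capsule, so the draw follows it.
- Post-op arm: the first capsule is placebo and ZNS is the second. The two intervals overlap and nothing orders them, so the draw may precede ZNS.

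With 78 subjects per arm, this could affect up to 78 of 78 + 78 = 156 subjects on ZNS. The wording of the draw time also differs: the SAP 2.6 footnote puts it at 12 hours after the first dose, the Protocol within 12 hours of it, and SAP 8.1.1 does not say which dose.

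**4. Repeat tests.** SAP 8.1.1 repeats abnormal tests until normal. SAP 5.1 keeps repeats out of summary tables unless specified. SAP 8.2 says nothing about which value counts.

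**5. Adverse event window**

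| Place | End of window |
|---|---|
| Protocol 6.0; SAP 4.3; SAP 8.1.1 | Two weeks post dose |
| Protocol 8.0 | Two weeks, plus the 30-day visit |
| Protocol 9.0 and SAP 2.6 calendars | Assessment marked at the 30-day visit |
| Protocol 11.1; SAP 8 | None stated |

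Taking the dose as close to the day of surgery, two weeks is day 14 and the visit falls on day 27 to 33. The interval between them is 27 − 14 = 13 to 33 − 14 = 19 days, nominally 30 − 14 = 16.

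**The case against.** A reader might infer that the SAP tabulates and lists screening labs only, stops adverse events at two weeks, and so leaves treatment effects unreported. The documents do not support that.

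- On listings, SAP 8.2 and 5.1 promise all results and all assessments. The by-group summary sentence in 8.2 names no visit, whereas 8.3 and 8.4 tie theirs to screening. The index is of proposed outputs, and SAP 11.1 develops the specifications later, with client review.
- On adverse events, SAP 8 summarizes all of them, no table or listing title carries a two-week limit, and the SAP's own calendar assesses them at the 30-day visit. The two-week sentences concern evaluation or tracking of drug-related events; they are not an exclusion rule. Nor is this simply the SAP departing from the Protocol, because Protocol 6.0 gives the same two weeks.
- On oversight, abnormal post-dose values reach the PI, and the DSMB reviews toxicities at least every six months.

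All of this stands, and it turns an apparent exclusion into a conflict. The 13 to 19 days are likewise days on which the passages disagree; no output is shown to drop them. What the objection does not supply is a specified post-dose or change-from-screening comparison by arm. A general listing rule does not provide one. Nor would quality control find the gap: under SAP 11.2, two programmers work to the same agreed specifications, so both would produce the same screening table.

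**Conclusion.** The point holds as a reporting gap and an inconsistency. The post-dose panel (eight parameters in SAP 8.2, planned for 234 subjects) has no named table or listing, and the SAP text and index disagree about whether it will be listed. The adverse event window has no single definition within or between the documents, and the treatment-emergent tables depend on one.

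The primary analysis is not affected, and it does not follow that safety findings would be lost. The post-op arm limits what the correction can deliver: unless draw time is shown against each capsule, a by-arm table may present pre-ZNS values as post-treatment ones.

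The conclusion assumes that the index titles are followed as written. The interval in days assumes dosing close to the day of surgery.

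**What to change.** **Laboratory outputs.**
- Amend SAP 8.2, Table 14.3.2 and Listing 16.3.2.1 to cover screening, post-dose and change from screening by arm, with shifts outside the normal range.
- Show the time of the draw relative to each capsule, and mark post-op-arm samples drawn before the second capsule.
- State how repeats are handled, for example the first post-dose value in the table and every repeat in the listing.
- Reconcile the draw-time wording in SAP 2.6 and 8.1.1 with Protocol 5.5, 5.6 and 9.0.

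**Adverse events.** Reconcile Protocol 6.0, 8.0, 9.0 and 11.1 with SAP 2.6, 4.3, 8 and 8.1.1, and define treatment-emergent in the SAP with one window that all the adverse event tables use. The study team must choose the window; what matters statistically is that it is fixed before unblinding.

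**Cost.** One revised table shell, one revised listing shell, a rewritten SAP 8.2 and short text edits in both documents. The laboratory results are already collected and no additional draw is needed. The timing display assumes that the clock times of the draw and both capsules are recorded. The documents do not confirm this, so the case report form should be checked first.

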8.3 Clinical Examination of the Ears

A clinical examination of ears will be performed at screening. Overall results will be recorded as Normal, Abnormal Not Clinically Significant, or Abnormal Clinically Significant.

The frequency and relative frequency of the overall assessment of the clinical examination will be summarized for screening visit by treatment group.

Clinical examination results will be listed.

8.4 Electrocardiogram (ECG)

A ECG was to be performed at screening for all subjects prior to protocol version 7.0, and no longer performed with changes in protocol 7.0. EGC parameters include heart rate, PR Interval, RR Interval, QRS Duration, QT Interval, and QTcF. Actual values of each ECG parameter at the screening visit will be summarized using descriptive statistics if requested upon final analysis.

All ECG results will be listed if requested upon final analysis.

8.5 Pregnancy Test

A pregnancy test (serum/urine) will be performed in female subjects of childbearing potential at screening. Pregnancy test results will be listed.

9 INTERIM ANALYSIS

A sponsor blinded interim analysis focused on the primary endpoint after 33% of the patients have completed participation in the study (26 in each group). The independent programmer will prepare the datasets for each pairwise comparison (subsets of data) using a pre-prepared SAS code and will freeze them for the interim analysis. To ensure the double blinding of the study the subjects will not be presented in the assigned groups. The blinded statistician will estimate the overall proportion of PTS positive subjects in each group. Then one-sided Fisher's exact test will be used to compare the proportion of subjects with PTS positive in ZNS group with the proportion of patients with PTS positive in the placebo group. one-sided p-value (p_i) from Fisher's Exact Test will be converted to a z-value using the inverse Normal transformation [1,2], i.e. $z_i = \Phi^{-1}(1 - p_i)$, where $\Phi^{-1}(\cdot)$ represents the inverse standard Normal cumulative distribution function.

For each pair-wise comparison, with 33% information, the trial would be stopped for futility if the interim z-value ≤ 0.6850 for either or both comparisons, corresponding to a conditional power of $\leq 10\%$ for each comparison. This design would provide 79.6% overall power (i.e. the probability of passing futility and reaching p ≤ 0.0125 for one or both comparisons in the final analysis would be 79.6%).

Based on interim analysis the following actions may be taken:

- Stop only one of the ZNS groups for futility
- Stop the trial (both ZNS groups) for futility
- Continue the trial as planned.

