#### 11.0 DATA AND SAFETY MONITORING

In compliance with the Washington University Institutional Data and Safety Monitoring Plan, an independent Data and Safety Monitoring Board (DSMB) will be specifically convened for this trial to review toxicity data. A DSMB will consist of no fewer than 3 members including 2 clinical investigators and a biostatistician. Individuals invited to serve on the DSMB will disclose any potential conflicts of interest to the trial principal investigator and/or appropriate university officials, in accordance with institution policies. Potential conflicts that develop during a trial or a member's tenure on a DSMB must also be disclosed.

The DSM report for the DSMB will be prepared by the study team with assistance from the study statistician, will be reviewed by the DSMB, and will be submitted to the PI. The DSM report will be prepared for the DSMB semi-annually and at other times at the discretion of the DSMB. The DSMB must meet at least every six months beginning six months after enrollment of the first participant at the secondary site, no more than one month prior to the due date of the DSM report to the PI. This report will include:

- HRPO protocol number, protocol title, Principal Investigator name, data coordinator name, regulatory coordinator name, and statistician
- Date of initial HRPO approval, date of most recent consent HRPO approval/revision, date of HRPO expiration, date of most recent QA audit, study status, and phase of study
- History of study including summary of substantive amendments; summary of accrual suspensions including start/stop dates and reason; and summary of protocol exceptions, error, or breach of confidentiality including start/stop dates and reason
- Study-wide target accrual and study-wide actual accrual
- Protocol activation date at each participating site
- Average rate of accrual observed in year 1, year 2, and subsequent years at each participating site
- Expected accrual end date, accrual by site, and accrual by cohort
- Objectives of protocol with supporting data and list the number of participants who have met each objective
- Measures of efficacy
- Early stopping rules with supporting data and list the number of participants who have met the early stopping rules
- Power analysis and/or interim analysis (if described in the protocol)
- Summary of toxicities
- Abstract submissions/publications
- Summary of any recent literature that may affect the safety or ethics of the study

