2.5 Treatment Assignment and Blinding

To ensure double-blinding of the trial, each subject will be randomized to one of three treatment arms via an interactive randomization tool (IRT) and assigned to a study group. Once randomized, each subject will be provided a kit on the day of surgery that contains two bottles, with one package labeled to be taken prior to surgery, and another package designated to be taken within 12 hours after surgery or when patient is released clinically to oral medication. For subjects randomized to "ZNS pre-op", the pre-op package will contain one ZNS capsule of 100 mg, and the post-op package will contain one placebo capsule that looks and tastes the same as ZNS capsules. For subjects randomized to "ZNS post-op", the pre-op package will contain one placebo capsule and the post-op package will contain one ZNS capsule of 100 mg. For the subjects randomized to "placebo", both pre- and post-op packages will contain capsules of placebo.

The study will be "masked" or "blinded" in the sense that all the study subjects and the study team members will be blinded to the assignment in the study groups. Only the pharmacist who will prepare the study drug kits and the unblinded Statistician will have access to the kit assignments. A copy of the randomization kit list with study ID assignments will be saved in a limited access folder on a secure network server at Pharm-Olam. The Medical Monitor will be contacted in emergent medical cases when knowing the treatments assignment is mandatory for clinical care of the patient.

At the time when we will need to "freeze" the data sets for purposes of developing the DSMB report, a series of SAS programs will be run from an independent programmer to produce data for each pairwise comparison into two subsets of data from the total cohort. Each subset will be de-identified. A previously prepared SAS code will be run in each subset and the output will be used to complete the table shells. Table shells will be blinded. If DSMB members find any safety issues, they may request specific unblinded data. The programmer preparing subsets will not be involved in the handling of data forms or the analysis of data. Table shells for DSMB (content and formats) will be agreed upon prior to start of study.

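### Masking of comparative interim results cannot be maintained as written: placebo is in both pairwise data sets, and the blinded study team prepares the DSMB report

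*SAP*

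**What the plan says.** **Shared comparator.** SAP 2.3 makes placebo the common control for both ZNS groups.

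**How data are cut.** SAP 2.5, with matching text in Protocol 4.0, has an independent programmer run code "to produce data for each pairwise comparison into two subsets of data from the total cohort". The subsets are de-identified, the analysis code is written in advance and the table shells are masked. The programmer is kept out of data-form handling and analysis. Study team members are to be blinded, and only the pharmacist and the unblinded statistician have access to kit assignments.

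**Interim.** SAP 9 and Protocol 12.4 say that subjects will not be shown by assigned group. The next sentence is: "The blinded statistician will estimate the overall proportion of PTS positive subjects in each group". SAP 9 then specifies a one-sided Fisher test of ZNS against placebo, converted to a z-value and compared with 0.6850. The first listed action is "Stop only one of the ZNS groups for futility".

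**Reporting.** Protocol 11.0 states: "The DSM report for the DSMB will be prepared by the study team with assistance from the study statistician". SAP 1 repeats this. The DSMB reviews the report, which is then submitted to the PI. Protocol 11.0 lists efficacy measures among its contents, and also the interim analysis where the protocol describes one, which section 12.4 does. Neither document describes a closed report restricted to the DSMB.

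**The concern.** The masking relies on group labels being hidden, but the structure of the outputs gives one label away. Two pairwise data sets drawn from three arms with a common control must be pre-op plus placebo and post-op plus placebo. The group that occurs in both is placebo.

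Two further features add to this. The interim needs estimates by group and a directional comparison, yet the only person named for any of that work is called blinded. The DSMB report is also assembled by people who are required not to know comparative results.

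What is at stake is knowledge of interim event rates by group among those running the trial. They keep discretion while it runs: Protocol 12.4 and SAP 4.4 allow eligibility criteria to be revised if accrual is slow, and SAP 1 allows the SAP to be modified on DSMB feedback. Decisions of that kind should be made without knowledge of how the arms compare.

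**Working it through.** **Inputs.** From SAP 2.7: 78 per arm, placebo PTS rate 50%, ZNS rate 25%, one-sided alpha 0.0125 per comparison. From SAP 9: 26 per group at the interim and a futility boundary of z = 0.6850. The ZNS rates of 40% and 50% used below are assumptions, to show a range.

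**Step 1: the plan's own figures.**
- Power: sum Bin(x; 78, 0.25) × Bin(y; 78, 0.50) over all pairs (x, y) whose one-sided Fisher p-value is at most 0.0125. Result 80.7%, against the stated 80.4%. Reproduced.
- Interim size: 3 × 26 = 78, and 78/234 = 33%. Reproduced.
- Boundary: conditional power under the current trend is Φ((z/√t − 2.2414)/√(1 − t)). With z = 0.685 and t = 1/3 this is Φ((1.186 − 2.241)/0.816) = Φ(−1.29) = 9.8%, consistent with the stated 10% or less. The two-sided p-value is 0.493, against the 0.49 in Protocol 12.4. Reproduced.

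The numerical design is therefore not in question here. The issue is who sees what.

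**Step 2: can placebo be found from masked counts?** Let X, A and B be the PTS counts in placebo, pre-op and post-op. One output shows X and A, the other X and B, all unlabelled. The count common to both is X. This is ambiguous only when A = B and both differ from X, because the two outputs are then identical. With independent binomial counts on 26 subjects per arm:

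P(placebo count identified) = 1 − Σₖ P(A = k) P(B = k) [1 − P(X = k)]

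| Placebo / pre-op / post-op rate | Identified | Ambiguous |
|---|---|---|
| 50 / 25 / 25% (planning effect in both) | 0.874 | 0.126 |
| 50 / 50 / 50% (no effect) | 0.904 | 0.096 |
| 50 / 25 / 40% | 0.942 | 0.058 |
| 50 / 25 / 50% (one arm works) | 0.982 | 0.018 |

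At 78 per arm the same formula gives 0.926, 0.941, 0.991 and 0.9997. These figures use the PTS count alone. Any further column, or records that can be linked across the two files, would make matching easier.

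**Step 3: does the test need direction?** Take 7/26 against 13/26.
- If the 7 are ZNS, one-sided p = 0.077 and z = 1.43. This is above 0.6850, so the arm continues.
- If the 7 are placebo, p = 0.978 and z = −2.01. This is below 0.6850, so the arm stops.

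The same two counts lead to opposite decisions. Either the analyst or the code must carry the placebo label. If the code carries it, a reader who has the two counts and the sign of z can recover the label.

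**Step 4: roles side by side.** SAP 2.5 requires the study team to be blinded, while Protocol 11.0 and SAP 1 make that team the author of the DSM report. SAP 2.5 names an unblinded statistician, but neither SAP 9 nor Protocol 12.4 gives that person the interim.

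**The case against.** The plan does contain safeguards: an independent programmer, de-identified subsets, frozen data, pre-written code and masked shells. The look is for futility only, so no early efficacy claim is possible. The Fisher sentence in SAP 9 is passive and names nobody, and the listed actions name no decision-maker. Pre-written code could embed the comparator, so whoever runs it need not be told the label. Protocol 11.0 lists efficacy measures without saying that they are shown by arm, and Protocol 4.0 says that groups in the shells are not identified.

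Much of this stands, and it limits what can be said.

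- A reader might infer that the blinded statistician is instructed to run the test and choose which arm stops. The text assigns that person only the estimates by group. The rest is the natural reading, not a stated duty.
- A reader might infer that matching results always reveal placebo. From counts alone, about 2% to 13% of trials stay ambiguous in the scenarios above. Near-certainty would need records linkable across files, and the documents say only that the subsets are de-identified.
- A reader might infer that audiometric testing or the classification of protocol deviations is compromised. Either would need knowledge of individual allocations. Aggregates do not supply it, the kit list stays restricted, and SAP 6.6 places deviation classification at a blinded review. The two ZNS arms also remain indistinguishable unless the comparisons are labelled.

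The safeguards do not remove the shared arm. Hiding labels does not help when the repeated group identifies itself, and none of the safeguards changes who prepares or receives the report.

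**Conclusion.** The point holds in a limited form: as written, the plan cannot assure that comparative results stay masked. It would go too far to say that the trial's blinding has failed. With masked counts only and 26 per arm, the placebo group can be inferred in about 87% to 98% of trials. This assumes independent binomial counts, equal group sizes, a placebo rate of 50%, ZNS rates between 25% and 50%, and both pairwise outputs being seen by the same person. That last condition is met by anyone who estimates the rates for both comparisons. It would also be met by the study team if the masked tables pass through its hands into the report, as the stated routing implies.

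What could become known is the placebo event rate and how the two ZNS groups compare with it. This could influence trial conduct or later changes to the plan. Leakage of individual allocations is not shown, and the size of any bias cannot be derived from the documents. The contradiction is real and inexpensive to repair, so it should be fixed before the interim.

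**What to change.** 1. In SAP 9 and Protocol 12.4, assign the interim analysis (estimates by group, Fisher test, z-value and comparison with the boundary) to the existing unblinded statistician. Remove the blinded statistician from this step and say who receives the result.
2. In SAP 2.5 and Protocol 4.0, give all by-group DSMB tables to the same unblinded statistician. The independent programmer should not take on this work, because both sections bar that role from the analysis of data. The same sections should state what access the programmer has: cutting pairwise data sets requires knowing the arms, yet the access list names only the pharmacist and the unblinded statistician.
3. In Protocol 11.0 and SAP 1, split the DSM report. A closed part, with by-group efficacy, safety and interim results, goes to the DSMB only. An open part, with data pooled over arms, is prepared by the study team. The study team and PI receive the open part and the DSMB's recommendation, and nothing by group.

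**Cost.** Wording changes in six sections, a changed route for reports and some added work for the unblinded statistician, whose capacity the sponsor should confirm. Sample size, alpha, futility boundary and power are unaffected.
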